Short Forearm Casting Versus Below-elbow Splinting for Acute Immobilization of Distal Radius Fractures

NCT02679066

November 13, 2015

JHM IRB - eForm A – Protocol

- **Use the section headings to write the JHM IRB eForm A, inserting the appropriate material in each. If a section is not applicable, leave heading in and insert N/A.**
- **When submitting JHM IRB eForm A (new or revised), enter the date submitted to the field at the top of JHM IRB eForm A.**

1. Abstract

- a. Provide no more than a one page research abstract briefly stating the problem, the research hypothesis, and the importance of the research.

Problem:

There is no consensus regarding the need to immobilize the elbow in immediate immobilization of closed distal radius fractures post-reduction. Decreased functionality of the upper extremity is a notable morbidity associated with below-elbow splinting of distal radius fractures post-reduction. Few studies have provided evidence comparing sugar tong splinting versus short-arm casting as methods of immediate post-reduction immobilization.

Research Hypothesis:

There is no significant difference in maintenance of reduction, changes in radiographic parameters, or functional scores at two weeks in patients with distal radius fractures treated acutely with a short arm cast versus a sugar tong splint.

Importance:

The study will provide guidance regarding the need for short forearm cast immobilization versus sugar tong splinting in early maintenance of reduction of closed distal radius fractures, as well as functional effects of sugar tong splinting versus short forearm casting.

2. Objectives (include all primary and secondary objectives)

To determine the success of sugar tong splinting versus short arm casting for maintenance of reduction of closed distal radius fractures and to compare the functional outcomes in patients treated with sugar tong splinting versus short forearm casting as guidance for immediate post-reduction immobilization of these fractures.

Primary objectives:

3. Background (briefly describe pre-clinical and clinical data, current experience with procedures, drug or device, and any other relevant information to justify the research)

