- a. Study design, including the sequence and timing of study procedures (distinguish research procedures from those that are part of routine care).
 - b. Study duration and number of study visits required of research participants.
 - c. Blinding, including justification for blinding or not blinding the trial, if applicable.
 - d. Justification of why participants will not receive routine care or will have current therapy stopped.
 - e. Justification for inclusion of a placebo or non-treatment group.
 - f. Definition of treatment failure or participant removal criteria.
 - g. Description of what happens to participants receiving therapy when study ends or if a participant's participation in the study ends prematurely.
- Prospective, randomized, controlled trial
 - One hundred twenty adult patients with closed fractures of the distal radius will be randomized to below-elbow, sugar-tong splinting versus short arm casting for immediate post-reduction immobilization.
 - Residents will undergo a teaching session specifically for instruction on sugar tong splinting versus short arm casting. On-call resident will have access to an electronic folder containing randomization of patient to sugar tong splint versus bivalved short arm cast. All reductions will be performed under local hematoma block with 1% lidocaine and traction and less than three attempts at reduction.
 - Patients will follow up at one, two and four weeks for repeat AP and lateral radiographs of the forearm to measure radiographic parameters to determine maintenance of reduction and will complete the Disabilities of the Arm, Shoulder and Hand Score (DASH) for functional scoring of the upper extremity at two weeks.
 - Maintenance of reduction, as defined below, will be compared between splint constructs overall and in stable versus unstable fractures in each immobilization group. Specific changes in radial height, radial inclination and volar tilt as continuous variables will also be compared, as will DASH scores measuring functionality.
 - Maintenance of reduction will be defined as: loss of reduction of < 2 mm radial height, < 5 degrees of radial inclination or < 10 degrees of volar tilt and/or < 2 mm intra-articular step off, in follow up radiographs as compared to immediate post-reduction radiographs (Koval et al., 2006).

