 - Unstable fractures will be defined as, at injury: > 4 mm radial shortening, > 10 degrees dorsal tilt, radial-ulnar translation of radius > 2 mm, dorsal comminution > 50% diameter of radius, > 2mm intra-articular displacement (Koval et al., 2006; Stoffelen and Broos, 1998). Fractures meeting these criteria will undergo ORIF after reduction and at a later time. However, reduction parameters and maintenance of reduction will be evaluated and compared for both splinting techniques until ORIF.

5. Inclusion/Exclusion Criteria

- Inclusion criteria: adult > 18 years of age, closed fracture, isolated injury, no prior injury to ipsilateral forearm, less than or equal to two attempts at reduction.

6. Drugs/ Substances/ Devices

- a. The rationale for choosing the drug and dose or for choosing the device to be used.
- b. Justification and safety information if FDA approved drugs will be administered for non-FDA approved indications or if doses or routes of administration or participant populations are changed.

- c. Justification and safety information if non-FDA approved drugs without an IND will be administered.

Not Applicable

7. Study Statistics

- a. Primary outcome variable.
- b. Secondary outcome variables.
- c. Statistical plan including sample size justification and interim data analysis.
- d. Early stopping rules.

Primary outcome variable: Maintenance of reduction

Secondary outcome variables: Radiographic parameters analyzed individually: radial height, radial inclination, volar tilt, DASH scores

Statistical plan including sample size: Sample size was calculated based on standard deviations for the above-noted outcomes variables reported in the literature and selected a sample size based on the largest calculated sample size. This was increased from 167 to 200 to account for expected dropout.

Early stopping rules: Less than 50% patient follow-up.

8. Risks

- a. Medical risks, listing all procedures, their major and minor risks and expected frequency.
- b. Steps taken to minimize the risks.
- c. Plan for reporting unanticipated problems or study deviations.
- d. Legal risks such as the risks that would be associated with breach of confidentiality.
- e. Financial risks to the participants.
 - No medical risks outside of standard of care.
 - Patients will be treated with standard of care.
 - Research committee of Department of Orthopaedic Surgery follows the progress of the project.
 - No legal risks.
 - No financial risks.

9. Benefits

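### The primary outcome has no visit and ORIF has no outcome status, so an unstable fracture may count as maintained on its week-1 film alone

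*Combined protocol and SAP*

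**What the plan says.** - **Outcome (Section 7).** The whole entry is "Primary outcome variable: Maintenance of reduction". No visit is attached.
- **Films (Section 4).** "Patients will follow up at one, two and four weeks for repeat AP and lateral radiographs". Maintenance is judged "in follow up radiographs as compared to immediate post-reduction radiographs". The text does not say which film decides or how several films combine.
- **Time anchor (Section 1, research hypothesis).** The hypothesis is of "no significant difference in maintenance of reduction, changes in radiographic parameters, or functional scores at two weeks". The closing time phrase can be read as covering all three outcomes or only the last. It is not carried into Section 7.
- **Unstable fractures (Section 4).** They are defined by at-injury criteria, and Section 5 does not exclude them. "Fractures meeting these criteria will undergo ORIF after reduction and at a later time". Until then, "reduction parameters and maintenance of reduction will be evaluated and compared for both splinting techniques until ORIF".
- **Comparisons (Section 4).** Maintenance is compared between the two constructs in all patients together, and also by stability within each immobilization group.
- **Unanswered template item (Section 4, item f).** "Definition of treatment failure or participant removal criteria" is printed, but no answer follows.

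**The concern.** A stable fracture can be watched for four weeks. An unstable one is watched until an operation whose date is not stated. Both enter one pooled proportion, so the primary outcome can rest on unequal observation windows, with the shorter window in the fractures that the plan itself calls unstable.

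If ORIF falls between the week-1 and week-2 films, two analysts could both follow the text and treat the same patient differently: one scores the week-1 film, the other excludes the patient. If ORIF comes before week 1, there is no scheduled follow-up film at all. The two-week DASH has a parallel gap, because nothing says how a score taken after ORIF is handled.

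The direction matters. Scoring on the last available film misses later losses and tends to shrink the difference between arms. The hypothesis is one of no difference, so lost signal favours it.

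**Working it through.** **No figure in the plan to reproduce.** The documents give no loss rate, no share of unstable fractures and no ORIF timing. Every rate below is an assumption, used only to gauge size. The totals come from the documents: 120 (Section 4) and 200 (Section 7), that is 60 or 100 per arm if allocation is 1:1. That the two totals differ is a separate matter.

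**Step 1: two-week loss.** Assume four-week loss p4 of 30% versus 45% with constant hazard, so p2 = 1 − (1 − p4)^(1/2).
- 1 − 0.70^0.5 = 16.3%
- 1 − 0.55^0.5 = 25.8%
- Difference: 9.5 points

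**Step 2: week-1 loss.** Let s be the share of the two-week cumulative hazard that falls in week 1, so p1 = 1 − (1 − p2)^s.
- s = 0.5 (constant hazard): 8.5% versus 13.9%, difference 5.35 points
- s = 0.8 (front-loaded): 13.3% versus 21.3%, difference 7.97 points

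**Step 3: scoring a share f of all patients on week 1.** Observed difference = (1 − f) × 9.50 + f × (week-1 difference). A share of 7.5% corresponds to 30% unstable with 25% of them operated on early (0.30 × 0.25). A share of 25% corresponds to 50% unstable with 50% operated on early.

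| f | s = 0.5 | s = 0.8 |
|---|---|---|
| 7.5% | 0.925 × 9.50 + 0.075 × 5.35 = 9.2 | 9.4 |
| 25% | 0.75 × 9.50 + 0.25 × 5.35 = 8.5 | 9.1 |

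**Step 4: power** (two-sided 0.05, unpooled normal approximation, s = 0.5, f = 0 / 7.5% / 25%).
- 60 per arm: 25% / 24% / 22%
- 100 per arm: 38% / 37% / 34%

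**Step 5: higher hazard in unstable fractures.** Let half the fractures be unstable with three times the hazard, keeping overall two-week loss at 16.3% and 25.8%. With x the stable two-week survival, solve 0.5(1 − x) + 0.5(1 − x³) = p2, giving x = 0.9128 and 0.8560.
- Stable loss S = 1 − x: 8.7% and 14.4%
- Unstable loss by week 2, L2 = 1 − x³: 23.9% and 37.3%
- Unstable loss by week 1 at s = 0.5, L1 = 1 − x^1.5: 12.8% and 20.8%

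Let half the unstable fractures in each arm have ORIF between weeks 1 and 2, unrelated to displacement.
- Last film, 0.5S + 0.5(0.5·L2 + 0.5·L1): 13.5% versus 21.7%, difference 8.2 points
- Early ORIF excluded, (0.5S + 0.25·L2)/0.75: 13.8% versus 22.0%, difference 8.2 points

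**Step 6: limit of censoring.** Suppose ORIF timing is informative: 70% of unstable fractures about to displace in week 2 are operated on first, but only 30% of the others. With d = L2 − L1, the censored week-2 hazard is 0.3d / (0.3d + 0.7(1 − L2)), which is 0.059 and 0.101. Unstable loss is then 1 − (1 − L1)(1 − hazard), or 17.9% and 28.8%. Averaged equally with stable loss this gives 13.3% versus 21.6%. The difference is 8.3 points against a true 9.5.

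**Step 7: change scores (separate point).** Variance of the baseline-adjusted analysis over that of the change score = (1 − ρ²)/(1 + k² − 2ρk), where k is baseline SD over follow-up SD. At k = 1 this equals (1 + ρ)/2, or 0.65 to 0.90 for ρ from 0.3 to 0.8. At k = 0.5 and ρ = 0.5 it is 0.75/0.75 = 1.00, no gain.

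**The case against.** **The plan says more than it may seem.** The hypothesis mentions two weeks, and reading that over the whole list is at least as natural as limiting it to function. This stands, and a claim that the plan gives no time anchor at all would be wrong. It does not close the gap. With two weeks as the visit, a fracture operated on between weeks 1 and 2 still has no status.

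**Following patients until ORIF is itself a rule.** Judging a splint or cast only while it is worn is a legitimate target. This stands in part. The rule says when observation ends, but not whether the patient then counts on the last film, is censored or is excluded.

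**The effect is small.** At shares of 7.5% to 25% the loss is about one point or less in the simple model (1.3 points in Step 5), and power at 60 per arm falls by one to three percentage points. Larger shrinkage would need half or more of all patients to be last seen at week 1, for which the documents give no support. Stable fractures are not assigned ORIF, so their comparison is largely untouched. All of this stands.

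**A stronger reading.** A reader might infer that the result could swing widely, by counting early ORIF as lost and letting its timing differ between arms. With no true difference (21% loss in both arms) and early ORIF in 25% versus 75% of unstable fractures, that scoring gives 17.4 points. The documents do not support it. ORIF follows at-injury criteria, so it is not evidence of lost reduction. The text does not suggest such scoring, and nothing in it gives a reason to expect so large a timing gap between randomised arms.

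**Conclusion.** The concern holds as a gap in the outcome definition with a foreseeable consequence. ORIF is planned for a whole enrolled class, so unequal observation in the pooled primary comparison follows from the plan's own design. The textual point is certain; its size is not.

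Under the assumed rates, shrinkage is small to modest: 9.5 points to 9.2 or 8.5, or to 8.2 if unstable fractures carry three times the hazard, and to only 9.4 or 9.1 if loss is front-loaded in the simple model. These figures rest on the assumed loss rates, unstable share and early-ORIF share.

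A reader might also infer that the plan prescribes scoring on the last film. It does not; it only leaves that open. The change is worth making because it is cheap and must be settled before the data are seen, not because a large bias has been shown.

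**What to change.** 1. **Visit.** In Section 7 name two weeks as the primary visit, to match the hypothesis, with weeks 1 and 4 secondary.
2. **ORIF rule.** Record the ORIF date. Do not score a patient operated on before the two-week film as maintained on an earlier film alone. Pre-specify one primary rule, for example two-week cumulative loss in the assigned immobilization, censored at ORIF and adjusted for stability at injury. Add two sensitivity bounds, with early-ORIF patients all lost and then all maintained, and report ORIF timing by arm. State that censoring assumes ORIF timing is unrelated to displacement given stability, and that patients operated on before week 1 contribute only to the bounds.
3. **Comparisons.** Adjust the pooled comparison for stability, and state the subgroup comparison as splint versus cast within each stratum.
4. **DASH.** Analyse the two-week score in all randomised patients and flag scores taken after ORIF.
5. **Separate free improvement.** Compare follow-up radial height, inclination and volar tilt adjusted for the immediate post-reduction value and stability, instead of raw changes. This gives 10–35% less variance if variances are equal and correlation is 0.3–0.8, and at worst about no gain.

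**Cost.** One added data item and revised text in Sections 4 and 7, with no new visit, film or questionnaire. The analysis needs slightly more modelling, and weeks 1 and 4 become secondary. Censoring recovers no power, because the follow-up cut off by ORIF stays unobserved, and it remains biased if timing is informative (Step 6), which is why the bounds are needed. No change to who has ORIF or when is proposed.

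### The primary outcome is yes/no, but 167 is justified only by literature standard deviations, so it is not shown to serve that outcome; a non-significant result should not be read as no difference

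*Combined protocol and SAP*

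**What the plan says.** Section 7 (Study Statistics) gives "Primary outcome variable: Maintenance of reduction". Section 4 (Study Procedures) defines it by thresholds on change from the post-reduction film: "Maintenance of reduction will be defined as: loss of reduction of < 2 mm radial height, < 5 degrees of radial inclination", followed by limits for volar tilt and step-off. Each patient is thus classed as having kept or lost reduction.

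The secondary outcomes in Section 7 are "Radiographic parameters analyzed individually: radial height, radial inclination, volar tilt, DASH scores". Section 4 separates the radiographic ones from the primary outcome by their scale: "Specific changes in radial height, radial inclination and volar tilt as continuous variables will also be compared".

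The sample size text in Section 7 says "Sample size was calculated based on standard deviations for the above-noted outcomes variables reported in the literature" and that the authors "selected a sample size based on the largest calculated sample size". The result, 167, is raised to 200 for dropout. The text does not name the outcome that produced 167, or say whether 167 is a total or a number per arm. It gives no standard deviation, expected rate, difference, margin, alpha, power or dropout rate. Section 4 gives another number: 120 patients to be randomised.

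The Research Hypothesis in Section 1 begins "There is no significant difference in maintenance of reduction". No equivalence or non-inferiority margin appears anywhere.

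**The concern.** A comparison of two proportions is sized from an expected proportion and a difference or margin. A standard deviation taken from the literature is the usual input for a continuous measure, and here the continuous measures are the secondary outcomes. A binary outcome does have a standard deviation, sqrt(p(1−p)), but it is fixed by p, and the plan states no p. The reader cannot tell what 167 achieves for the outcome on which the trial will be judged.

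This matters more than usual because the hypothesis is itself one of no significant difference. Followed as written, a non-significant test would count as confirming it, and the trial is meant to guide the choice of immobilisation. If the confidence interval is wide, the same result is compatible with a sizeable difference in loss of reduction.

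**Working it through.** **Inputs from the documents:** 167 before dropout and 200 after (Section 7); 120 randomised (Section 4); a yes/no primary outcome (Section 4).

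**Assumptions, because the documents are silent:** two-sided 5%, 80% power, 1:1 allocation, and maintenance of 60%, 70%, 80% or 90%. Whether 167 is a total or per arm is unknown, so both are shown.

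**Step 1: can 167 be reproduced?** No; its inputs are not stated. Working backwards from 167 in total (83.5 per arm):
- Two means: standardised difference = (1.96 + 0.84) × sqrt(2/83.5) = 0.43 at 80% power, or (1.96 + 1.28) × sqrt(2/83.5) = 0.50 at 90%.
- Two proportions: 60% vs 80% at 80% power needs 164 in total; 70% vs 90% at 90% power also needs 164.

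Both kinds of calculation arrive near 167, so the number does not reveal its own basis. The dropout step is reachable (1 − 167/200 = 16.5%, or 167 × 1.20 = 200.4), but the rate is not stated.

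**Step 2: precision for the primary outcome.** With n per arm and a common rate p,

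half-width = 1.96 × sqrt(2p(1−p)/n).

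For p = 0.70 and n = 83.5: sqrt(0.42/83.5) = 0.0709, and 1.96 × 0.0709 = 0.139, or 13.9 points.

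**Step 3: smallest fall detectable with 80% power.** Solve for Δ = p1 − p2, with p̄ the mean of the two rates:

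power = Φ{[Δ − 1.96 × sqrt(2p̄(1−p̄)/n)] / sqrt[p1(1−p1)/n + p2(1−p2)/n]} = 0.80.

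Results in percentage points, for maintenance of 60 / 70 / 80 / 90%:

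| Evaluable | 95% CI half-width | Smallest detectable fall |
|---|---|---|
| 167 in total | 14.9 / 13.9 / 12.1 / 9.1 | 21.5 / 21.1 / 19.7 / 16.7 |
| 167 per arm | 10.5 / 9.8 / 8.6 / 6.4 | 15.3 / 14.8 / 13.5 / 11.1 |
| 120 in total | 17.5 / 16.4 / 14.3 / 10.7 | 25.3 / 25.0 / 23.6 / 20.3 |

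The last row flatters the plan: 120 is the number randomised, and dropout would leave fewer evaluable.

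**Step 4: what a non-significant result would leave open.** Suppose 167 evaluable in total, rates near 70% and an observed difference of 5 points. The interval is 5 ± 13.9, or about −9 to 19 points: not significant, yet compatible with a 19-point difference.

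**Step 5: could a no-difference claim be supported?** Take a 10-point margin purely as an illustration. With equal true rates, the chance that the whole 95% CI lies within ±10 points is 2Φ(0.10/SE − 1.96) − 1, or zero where this is negative; SE = sqrt(2p(1−p)/n). With 167 in total it is 0% at 60%, 70% and 80% maintenance, because the half-width already exceeds 10 points. At 90% it is about 15%. The one-sided (non-inferiority) version, Φ(0.10/SE − 1.96), gives 26% to 58%, but that does not address a two-sided claim. If 167 is per arm and maintenance is 90%, SE = sqrt(0.18/167) = 0.0328 and the two-sided figure rises to about 72%.

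**The case against.** The strongest reply is textual. The sample size sentence refers to the outcome variables noted above it, and these include maintenance of reduction. Since the largest calculated size was taken, a calculation for the primary outcome may have been among the candidates, and 167 would then be at least as large as it required. Authors also use the term standard deviation loosely for published variability. Step 1 shows that plausible pairs of rates give about 167.

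This stands, and it limits the point. A reader might infer that 167 was derived from the continuous measures alone, that it fails to cover the primary outcome, or that it has no link to it. The documents support none of these: the outcome behind 167 is not named, and its inputs are not given.

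Three further objections are fair. If 167 is per arm, precision is noticeably better; the total reading is more natural beside the 120 of Section 4, but the plan does not settle it. The maintenance rates and the 10-point margin are illustrations, not figures from the plan. And unstated inputs alone would be incomplete reporting rather than a wrong analysis.

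The last objection does not dispose of the point, because the missing inputs combine with a hypothesis of no significant difference that has no margin. That combination affects the conclusion the trial would draw, whichever calculation produced 167.

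**Conclusion.** The point holds in a limited form: 167 is not shown to serve the yes/no primary outcome, and as the hypothesis is worded, a non-significant test would be taken as support for it while a sizeable difference remained possible.

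Over assumed maintenance of 60% to 90% with 1:1 allocation, 167 in total gives a half-width of about 15 to 9 points and a smallest detectable fall of about 22 to 17 points. On the per-arm reading these are about 10.5 to 6.4 and 15 to 11 points; with 120, about 18 to 11 and 25 to 20 points before dropout. The size of the problem therefore depends on the true rate and on which number applies. It is plain for a total of 120 or 167 at 60% to 80% maintenance, and milder at 90% or if 167 is per arm. That the sample size is wrong for the primary outcome is not established.

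**What to change.** 1. **Reporting rule.** Report the primary result as a difference in maintenance proportions with its 95% CI. Do not conclude that there is no difference from non-significance; draw that conclusion only if the CI lies within a margin fixed in advance and justified clinically by the investigators.
2. **Sample size text.** For the primary outcome, replace the standard deviation sentence with a two-proportion statement of what the planned number delivers at a stated rate, with alpha, power, allocation and dropout. If 167 evaluable in total is confirmed, it could read: with 167 evaluable and 70% maintenance, the difference is estimated to within about ±14 points. Keep the standard deviation calculations for the continuous secondary outcomes, and name the outcome that produced 167.
3. **Numbers.** Before stating that precision, reconcile the 120 of Section 4 with the 167/200 of Section 7, and say whether 167 is a total or per arm.

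The cost is wording and one calculation. The restatement needs no extra patients. The downside is a less favourable stated capability, and possibly having to accept that the trial can estimate the difference but not establish that there is none.

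### The increase from 167 to 200 allows for dropout only, yet evaluation of unstable fractures ends at ORIF, so fewer than 167 usable radiographs should be expected at any film taken after ORIFs begin, unless dropout is low enough to offset them

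*Combined protocol and SAP*

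**What the plan says.** Section 7 (Study Statistics) describes the basis of the size as follows: "Sample size was calculated based on standard deviations for the above-noted outcomes variables reported in the literature". The largest of the resulting sizes was taken, and then: "This was increased from 167 to 200 to account for expected dropout". It states no dropout rate, significance level, power, difference or standard deviation. It does not say which outcome gave the largest size, or whether 167 is a total or a number per arm. The primary endpoint is given as "Primary outcome variable: Maintenance of reduction", with no time point. The secondary outcomes are the individual radiographic parameters and DASH.

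Section 4 (Study Procedures) sets the films: "Patients will follow up at one, two and four weeks for repeat AP and lateral radiographs of the forearm". Maintenance of reduction "will be compared between splint constructs overall and in stable versus unstable fractures in each immobilization group", so unstable fractures belong to the main comparison. Section 5 has no stability criterion that would keep them out. Of unstable fractures, section 4 says: "Fractures meeting these criteria will undergo ORIF after reduction and at a later time". Until then they contribute data: "reduction parameters and maintenance of reduction will be evaluated and compared for both splinting techniques until ORIF".

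Section 4 also gives 120, not 200, as the number to be randomized. The hypothesis in section 1 refers to two weeks.

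**The concern.** The plan has two sources of missing radiographs and provides for one. Dropout is unplanned. ORIF is written into the protocol for a whole class of eligible patients, and it ends the evaluation of the primary outcome and of radial height, inclination and tilt. The losses compound, because a patient must both stay in the study and not yet have had ORIF to supply a usable film.

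A reader of section 7 would take 167 as the number left for analysis after losses. If it is not, the radiographic comparisons are less precise than that number suggests, increasingly so at later films as more ORIFs have been done. This matters more than usual because the section 1 hypothesis is one of no significant difference: fewer evaluable patients make a non-significant result more likely and easier to misread as support.

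**Working it through.** **Inputs.** From section 7: 167 and 200, read here as totals. From section 4: ORIF for all unstable fractures, evaluation of reduction until ORIF, films at weeks 1, 2 and 4. Not in the protocol, and therefore assumed: the share u of patients who have had ORIF by a given film.

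**1. Reproducing the plan's step.** The 167 cannot be recomputed, because its inputs are not given. The step to 200 can be checked. With N/(1 − d), the implied dropout is d = 1 − 167/200 = 0.165, and 167/0.835 = 200. The step is sound for dropout alone. If the planners instead used N × (1 + d), then d = 200/167 − 1 = 0.198, and at that rate 200 × (1 − 0.198) = 160 remain, already below 167. The rest uses 16.5%, the more favourable reading.

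**2. Reserve.** 200 × 0.835 = 167. Nothing is left over for a second loss.

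**3. Adding ORIF.** Evaluable number = 200 × 0.835 × (1 − u) = 167 × (1 − u).

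| Assumed share with ORIF by the film (u) | Evaluable of 200 | Illustrative power |
|---|---|---|
| 0% | 167 | 80% |
| 10% | 150 | 76% |
| 20% | 134 | 71% |
| 30% | 117 | 65% |
| 40% | 100 | 58% |

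The power column is Φ(2.80 × √(1 − u) − 1.96). It assumes that 167 is a total, that a radiographic outcome set it, and that it gave 80% power at two-sided 0.05. The plan states none of these.

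**4. How low dropout must be to compensate.** The largest ORIF share that still leaves 167 is 1 − 167/[200 × (1 − d)]:
- d = 15%: 1.8%
- d = 10%: 7.2%
- d = 5%: 12.1%
- d = 0%: 16.5%

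Even with no dropout at all, ORIF in more than 16.5% of patients before a film takes 200 below 167.

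**5. If 120 are randomized.** 120 is below 167 before any loss. After 16.5% dropout, 120 × 0.835 = 100 remain, before any ORIF.

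**The case against.** Several points on the other side have force.

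- **DASH may have set 167.** The size is the largest across outcomes that include DASH, and the sentence ending evaluation at ORIF concerns reduction, not DASH. If DASH was the driver, the radiographic outcomes needed fewer patients and have some slack. This stands against the power figures. It does not alter the count of usable films.
- **Patients contribute until ORIF.** A reader might infer that unstable fractures are lost to the analysis altogether. They are not. An analysis at a film before any ORIF, or at each patient's last film before ORIF, could still have 167. If every ORIF came after week 4, no film would be affected. The plan specifies none of these, so the possibility stands but cannot be relied on.
- **Dropout may have been meant to include ORIF.** The stated reason is only "to account for expected dropout", and nothing in the text extends this to planned surgery. If it was intended, a single allowance of 16.5% must cover both losses, and section 7 should say so.
- **Dropout accrues over time.** Applying the full 16.5% at week 1 or 2 may exaggerate loss at early films. This stands, and is one reason to state the number visit by visit.
- **167 and 200 could be per arm.** The table's counts would then apply to each arm. The proportional loss would be the same, and the conflict with 120 would be larger.

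**Conclusion.** The point holds for films taken after ORIFs begin. At the dropout that the plan's own figures imply, any ORIF before a film takes the number of usable radiographs at that film below 167, and only lower dropout can offset it. That follows from sections 4 and 7 alone. The size of the shortfall does not: about 150 to 100 evaluable patients is a range under assumed ORIF shares of 10% to 40%, with 200 randomized and 16.5% dropout among the rest.

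Two stronger readings should be resisted. One is that the trial's power is overstated by the amounts tabulated. Section 7 states no power, and the outcome that set 167 is unknown, so those percentages are only illustrative. The other is that the step from 167 to 200 is an arithmetic error. It is correct for dropout alone; what is missing is an allowance for a loss that the protocol itself plans.

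**What to change.** First reconcile the 120 to be randomized in section 4 with the 200 in section 7, since every count depends on it. Then, in section 7:

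1. Name the film used for the primary comparison, for example week 2 or the last film before ORIF.
2. State the number expected to be evaluable at weeks 1, 2 and 4 after both dropout and planned ORIF, using the department's own unstable share and ORIF timing, and give the dropout rate assumed.
3. State the resulting confidence-interval width or detectable difference for maintenance of reduction and for each radiographic parameter.
4. Do not treat 167 as the number available at films taken after ORIFs begin.

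The cost is a recalculation and a short addition to section 7. It requires the inputs behind 167 to be written down, and the stated figure will look less favourable. No extra enrolment is proposed, and nothing here bears on whether or when ORIF is done.
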